18.1.10. TEAEs LEADING TO NIVOLUMAB INFUSION RATE REDUCTION

TEAEs leading to nivolumab infusion rate reduction are those events recorded on the eCRF where “Action taken with nivolumab” is answered as “Infusion rate reduced”.

TEAEs leading to nivolumab infusion rate reduction will be presented by the following:

- SOC/PT & by cycle
- PT

Document: T:\sas\Debiopharm\Debio_1143\CZA60507\Biostatistics\Documentation\SAP\SAP Text\V5

Author: ██████████ Version Number: 5.0
Version Date: 19APR2022

Template No.: CS_TP_BS016 Revision 5
Effective Date: 01Apr2018

Reference: CS_WI_BS005

18.1.11. TEAEs LEADING TO NIVOLUMAB INTERRUPTION

TEAEs leading to nivolumab interruption are those events recorded on the eCRF where “Action taken with nivolumab” is answered as “Infusion interrupted”.

TEAEs leading to nivolumab interruption will be presented by the following:

- SOC/PT & by cycle
- PT

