If a patient does not meet the requirements for treatment continuation on any day other than D1 (D2-10 or D15-24) of any cycle, treatment will be immediately interrupted and the corresponding Debio 1143 dose (and nivolumab if on D15) will be omitted. Patients should be re-assessed, ideally, every 48-72 hours, if clinically indicated, and treatment will only be resumed after all re-treatment criteria are met. On D1, treatment can be delayed more than 3 days if required; in this case, the assessment schedule will shift accordingly, and all assessments planned for D1 will be performed on the day treatment is re-started. However, if treatment is interrupted during any day other than D1 and the re-treatment criteria are not met within 72 hours, treatment will be resumed only on D1 of the next cycle.

A maximum delay of 4 and 8 weeks (+1-week tolerance) for Debio 1143 and nivolumab, respectively, is allowed. After this delay-period, treatment will be withdrawn. Patients withdrawing from treatment for any reason will be followed for safety up to 5 months (±15 days) after the last nivolumab infusion, complete resolution or stabilization of any ongoing toxicity, unless the patient starts a new treatment, end-of-life-care or withdraws consent.

Patients experiencing immune-related AEs, that require withholding nivolumab infusions temporarily until resolution to at least Grade 1, may withhold nivolumab for a maximal period of up to 8 weeks (±1 week

tolerance). During this period, patients may continue to receive Debio 1143 as per protocol, if appropriate. Patients requiring more than 8 weeks ( $\pm 1$  week) of nivolumab interruption and those who permanently discontinue nivolumab for any reason, will discontinue Debio 1143 permanently and will be withdrawn from the study. The nivolumab dose will not be adjusted under any circumstances.

Patients experiencing any treatment-related grade 4 toxicity (clinically or laboratory, excluding grade 4 amylases and/or lipase and/or non-febrile neutropenia) will withdraw from treatment definitively without further reduction (see [section 8.3.2.1](#) for details).

Patients experiencing any other treatment-related toxicity fulfilling applicable DLT criteria (as shown below) at any time during the study must stop treatment and may only resume treatment after adequate recovery to re-treatment criteria.

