3.2. SECONDARY ENDPOINTS

Secondary endpoints for both study parts (unless otherwise specified) are:

- Incidence and severity of treatment-emergent adverse events (TEAEs) and clinical laboratory abnormalities, according to National Cancer Institute-Common Terminology Criteria for Adverse Events NCI-CTCAE version 5.0 criteria
- Changes in vital signs: systolic/diastolic blood pressure, heart rate (both after at least 5 minutes of supine rest), temperature, and weight; electrocardiogram (ECG) and Eastern Cooperative Oncology Group Performance Status (ECOG-PS)
- Incidence of premature treatment discontinuations and treatment modifications due to TEAEs and laboratory abnormalities (i.e., treatment compliance)
- Tumor response determined according to RECIST v1.1 and/or GCIG criteria (Cohort 4, if applicable):
 - Confirmed (Part A) and unconfirmed (Parts A and B) ORR
 - Disease control rate (DCR), defined as any response, partial or complete (PR or CR) + stable disease (SD)
 - Time-related endpoints as median time to response, median duration of response (DOR), median progression-free survival (PFS), PFS rate every months, median overall survival (OS), OS rate at 12 months and 18 months (if data allow)
- PK parameters of Debio 1143 and Debio 1143-MET1 as defined in the available population PK disposition model and, if appropriate, post-hoc estimates of areas under the curve (AUCs), C_{max}, and C_{min}; serum concentration versus time profiles of nivolumab and, if deemed appropriate, relevant nivolumab PK parameters derived from a population PK model.

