15. STUDY MEDICATION EXPOSURE

Exposure to any study medication, in weeks, will be presented for the RP2D (Part A only), SAF and EFF (Part B only) analysis sets.

The date of first study medication administration will be taken from the eCRF study drug exposure forms. The date of last study medication will be taken from the eCRF End of Treatment form.

The following information will be summarized in tables:

- Duration of exposure (weeks)
- Cumulative dose (mg), for cycle 1 and overall
- Number of administrations of Debio 1143, for cycle 1 and overall
- Number of infusions for Nivolumab (cycle 1 and full treatment period)
- Number of cycles for Nivolumab
- Details on treatment modifications
 - Number of patients having at least one Debio 1143 interruption, for cycle 1 and overall
 - Number of patients having at least one dose reduction (as defined in protocol section 5.4)
 - Summary of the number of interruptions of Debio 1143, for cycle 1 and overall
 - Summary of the number of patients having at least one interruption in the following durations (< 3 days, >= 3 days, >= 6 days, >= 14 days), for cycle 1 and overall
 - Summary of the cumulative duration of Debio 1143 interruption, for cycle 1 and overall
 - Incidence of action taken with Debio 1143/nivolumab and main reason for action taken

All exposure data as recorded exposure in the study drug exposure forms will be included in a listing. Also, data

Document: T:\sas\Debiopharm\Debio_1143\CZA60507\Biostatistics\Documentation\SAP\SAP Text\V5

Author: [REDACTED] Version Number: 5.0
Version Date: 19APR2022

Template No.: CS_TP_BS016 Revision 5
Effective Date: 01Apr2018

Reference: CS_WI_BS005

Copyright © 2009, 2010, 2012, 2016, 2018 IQVIA. All rights reserved. The contents of this document are confidential and proprietary to IQVIA Holdings Inc. and its subsidiaries. Unauthorized use, disclosure or reproduction is strictly prohibited.

recorded in the Debio 1143 and nivolumab accountability eCRFs will be listed.

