15.1. DERIVATIONS

- Duration of exposure (weeks)
 - Debio 1143: $(\text{date of last dose of Debio 1143} - \text{date of first dose of Debio 1143} + 1) / 7$
 - Nivolumab: $(\text{date of last dose of nivolumab} - \text{date of first dose of nivolumab} + 1) / 7$
- Actual Cumulative dose
 - Debio 1143 (mg): sum of the actual administered dose across all dosing dates
 - Nivolumab (mg): sum of the total dose administered across all cycles, if an infusion was interrupted then the total volume infused will be used to calculate the effective mg quantity administered ($\text{planned dose} \times (\text{total volume infused} / \text{total volume prepared})$)
- For every unique interruption, defined as any occurrence of a 0 mg dose succeeding a non-0 mg dose, the duration of unique Debio 1143 interruption = $(\text{date of last day with Debio 1143 exposure form completed with actual dose of 0 mg} - \text{date of first day with Debio 1143 exposure form completed with actual dose of 0 mg}) + 1$

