18.1.8. TEAEs LEADING TO INTERRUPTION OF DEBIO 1143

TEAEs leading to interruption of Debio 1143 are those events recorded on the eCRF where “Action taken with Debio 1143” is answered as “Dose omitted” or “Treatment delayed”.

TEAEs leading to interruption of Debio 1143 will be presented by the following:

- SOC/PT & by cycle
- PT

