18.1.12. TEAEs LEADING TO DISCONTINUATION OF NIVOLUMAB

TEAEs leading to dose discontinuation of Nivolumab are those events recorded on the eCRF where “Action taken with Nivolumab” is answered as “Treatment permanently discontinued”.

TEAEs leading to dose discontinuation of Nivolumab will be presented by the following:

- SOC/PT & by cycle
- PT

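### SAP 18.1.11 counts only interrupted infusions, so nivolumab doses withheld, omitted or delayed for a TEAE enter no nivolumab action table by SOC and preferred term

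*SAP*

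**What the plan says.** The SAP has three TEAE tables keyed to the action taken with nivolumab:

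- 18.1.10, infusion rate reduction: "Action taken with nivolumab” is answered as “Infusion rate reduced".
- 18.1.11, interruption: "Action taken with nivolumab” is answered as “Infusion interrupted".
- 18.1.12, discontinuation: "Action taken with Nivolumab” is answered as “Treatment permanently discontinued".

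For Debio 1143, the table with the matching title (18.1.8) uses a different rule: "Action taken with Debio 1143” is answered as “Dose omitted” or “Treatment delayed".

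On exposure, SAP 15.1 states that "if an infusion was interrupted then the total volume infused will be used to calculate the effective mg quantity administered". SAP section 15 counts and times interruptions for Debio 1143. For nivolumab modifications it has one line, shared by both drugs: "Incidence of action taken with Debio 1143/nivolumab and main reason for action taken".

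The protocol allows a temporary nivolumab hold. Under section 5.4, patients with immune-related AEs that require it "may withhold nivolumab for a maximal period of up to 8 weeks", with a one-week tolerance, and may continue Debio 1143 meanwhile. Protocol 11.6.4.2 says that treatment delays will be summarized for nivolumab.

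The secondary endpoint concerned (SAP 3.2) is "Incidence of premature treatment discontinuations and treatment modifications due to TEAEs and laboratory abnormalities (i.e., treatment compliance".

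**The concern.** The word interruption means two different things in neighbouring tables. For Debio 1143 it means that doses were skipped or postponed. For nivolumab it means that an infusion already running was stopped, which in this protocol is chiefly the response to an infusion reaction.

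The protocol does not allow the nivolumab dose to be changed, so withholding or postponing a dose is the only dose-level modification short of stopping the drug. That modification has no nivolumab TEAE table. A reader of the clinical study report who opens the table on TEAEs leading to nivolumab interruption would expect to find events such as Grade 2 colitis or pneumonitis that led to a hold. Under the rule as written, the table would hold only events that stopped an infusion partway. At stake is the completeness, for nivolumab, of a stated secondary endpoint on tolerability.

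**Working it through.** No figure in the plan is in dispute, so the check sets the passages side by side.

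**1. Which nivolumab actions the protocol foresees, and which have a TEAE table**

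| Action on nivolumab | Protocol source | SAP TEAE table |
|---|---|---|
| Infusion slowed | 7.6.2.2, Table 7-1 | 18.1.10 |
| Infusion stopped partway | 7.6.2.2, Table 7-1 | 18.1.11 |
| Dose withheld, omitted or delayed | 5.4, Tables 5-3 and 7-2 | none |
| Permanent discontinuation | 5.4, Tables 7-1 and 7-2 | 18.1.12 |

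Three of the four actions have a table.

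**2. What an interrupted infusion means.** SAP 15.1 computes the dose of an interrupted infusion from the volume infused relative to the volume prepared. That needs an infusion that was prepared and started. A skipped dose has no infused volume. Protocol Table 7-1 describes the same situation for a Grade 2 infusion reaction: stop, then resume at half the previous rate.

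**3. How widely the protocol provides for holds.** Entries of Table 7-2 that direct a temporary hold of nivolumab (entries that only ask the site to consider one are not counted):

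- gastrointestinal Grade 2 and first Grade 3 (2)
- skin first Grade 3 (1)
- pneumonitis Grade 2 (1)
- hepatic Grade 2 (1)
- renal Grade 2 (1)
- cardiac Grade 1 (1)
- endocrine Grade 3-4, and hypophysitis with moderate or worse symptoms or abnormal MRI (2)
- neurologic Grade 1, or peripheral neuropathy or mood changes up to Grade 2 (1)
- musculoskeletal Grade 2 (1)
- hematologic Grade 2 (1)
- ocular Grade 2 (1)

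Total: 2+1+1+1+1+1+2+1+1+1+1 = 13, with at least one in each of the 11 organ blocks.

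**4. Whether another output supplies the missing link**

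- *SAP 18.1.8 (Debio 1143 interruption).* Partly. When both drugs are held, the event can appear here. When Debio 1143 continues, as 5.4 permits, it need not. Even when it appears, the table records the action on Debio 1143.
- *SAP 18.1.16 (AESIs) and 18.1.5 (nivolumab-related TEAEs).* These show the events by SOC, preferred term and worst grade (AESIs also by cycle), but not the action taken.
- *SAP section 15, action taken and main reason.* This may count holds. The SAP does not specify a breakdown by SOC or preferred term.
- *SAP 16.1, compliance.* This equals actual dose / (cycles started × 480 mg) × 100. On the 240 mg schedule, one omitted Day 15 dose in a cycle gives (480 − 240)/480 = 50% for that cycle. A cycle that starts late but is given in full gives 480/480 = 100%, because a cycle runs until the next Day 1. Omissions lower the percentage, delays do not, and neither is tied to an event.

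**5. The delay summary.** Protocol 11.6.4.2 states one for nivolumab. SAP section 15 lists nivolumab exposure duration, cumulative dose, infusions, cycles and actions taken, but no delays. SAP 4.3, which lists changes from the protocol, does not mention this.

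**The case against.** The strongest reply is that little is lost.

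- The two drugs are coupled. Under Protocol 5.4, from Cycle 2 a patient who fails the re-treatment criteria on Day 1 has both drugs withheld, and a failure on Day 15 leads to omission of both. In Table 5-3 the transaminase, bilirubin and creatinine limits on Days 1 and 15 are the same for both drugs. Many hepatic and renal holds should therefore reach 18.1.8.
- Suspected immune-related AEs are nivolumab AESIs under Protocol 9.1.6 and are tabulated as such.
- The endpoint asks for an incidence, and section 15 gives an incidence of actions taken. Its layout may be finer in the table shells, which are separate documents.
- The eCRF response list for the nivolumab action is not in the documents. Protocol 5.4 itself uses the word interruption for a long nivolumab hold, so sites might record holds as interrupted infusions.
- Many Grade 3-4 rows of Table 7-2 call for permanent discontinuation, which 18.1.12 captures.

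Most of this stands, and it rules out two stronger readings. A reader might infer that withheld doses appear in no TEAE action table at all. The coupling of the drugs shows that some will appear in 18.1.8. A reader might also infer that immune-related toxicity goes unreported and that tolerability is thereby overstated. The AESI and nivolumab-related tables show the events, so the documents do not support that either.

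The reply does not restore the link between an event and a nivolumab hold. Capture through 18.1.8 depends on whether Debio 1143 was also held. If sites did record holds as interrupted infusions, 18.1.11 would mix them with infusion reactions and would still need splitting. The wording of SAP 15.1, and the separate omitted and delayed options for Debio 1143, argue against that recording, but do not settle it.

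**Conclusion.** The point holds as a reporting gap of limited reach. Read as written, SAP 18.1.11 gives a nivolumab interruption table that leaves out one of the four kinds of nivolumab action the protocol foresees. It also uses a narrower rule than the Debio 1143 table of the same name. The secondary endpoint on modifications due to TEAEs is therefore incompletely reported for nivolumab, mainly for Grade 2 and first Grade 3 events. Separately, the nivolumab delay summary in Protocol 11.6.4.2 has no counterpart in SAP section 15, and the omission is not declared in SAP 4.3.

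The number of affected patients cannot be derived. The 13 entries show how widely holds are provided for in a table of suggested management. They are not a forecast of events or a measure of bias. No futility or efficacy rule is touched.

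The conclusion assumes that an interrupted infusion means a partly given one, as SAP 15.1 implies, and that the unseen table shells do not already break down nivolumab actions by SOC and preferred term.

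**What to change.** 1. In SAP 18.1.11, define TEAEs leading to nivolumab interruption by every eCRF response on action taken with nivolumab that denotes an omitted, delayed or withheld dose, in parallel with 18.1.8. Keep the presentation by SOC and preferred term and by cycle.
2. Report interrupted infusions and infusion rate reductions separately, labelled as infusion-level actions.
3. Check the eCRF response list first. If it has no response for a withheld dose, a redefinition by response alone would give an empty table. In that case identify holds from the nivolumab exposure form and its recorded reason, link each to the concurrent TEAE where possible, and state how many could not be linked.
4. In SAP section 15, add the number and duration of nivolumab delays or omissions, as Protocol 11.6.4.2 foresees. If the summary is dropped on purpose, say so in SAP 4.3.

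The cost is SAP wording, one re-specified table, one added table for infusion-level actions and a few exposure rows. No new data are needed if the eCRF has the responses. Otherwise there is programming work and some medical review to match holds to events. This changes reporting only and leaves every dosing rule as it is.

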18.1.12. TEAEs LEADING TO DISCONTINUATION OF NIVOLUMAB

TEAEs leading to dose discontinuation of Nivolumab are those events recorded on the eCRF where “Action taken with Nivolumab” is answered as “Treatment permanently discontinued”.

TEAEs leading to dose discontinuation of Nivolumab will be presented by the following:

- SOC/PT & by cycle
- PT

18.1.13. SERIOUS ADVERSE EVENTS (SAEs)

SAEs are AEs recorded on the eCRF where “Was event serious?” is answered as “Yes”.

Treatment-emergent SAEs will be presented by the following:

- SOC/PT and relatedness to study drugs (related to Debio 1143, related to nivolumab and related to both)
- SOC/PT and by cycle

A separate listing of all SAEs will be presented.

18.1.14. TEAEs LEADING TO DEATH

TEAEs leading to death are those events recorded on the eCRF where the “Results in death” option is selected.

TEAEs leading to death will be presented by SOC/PT. A listing of all AEs leading to death will be presented.

18.1.15. MOST COMMON TEAEs

The analysis described in section 18.1.1 will be repeated but only presenting AEs where the overall percentage is $\geq 10\%$. Same analysis will be performed for AEs where the overall percentage is $\geq 5\%$. These will be presented by the

Document: T:\sas\Debiopharm\Debio_1143\CZA60507\Biostatistics\Documentation\SAP\SAP Text\V5

Author: [REDACTED] Version Number: 5.0
Version Date: 19APR2022

Template No.: CS_TP_BS016 Revision 5
Effective Date: 01Apr2018

Reference: CS_WI_BS005

following:

- SOC/PT and by cycle
- PT

18.1.16. ADVERSE EVENTS OF SPECIAL INTEREST (AESIs)

AESIs (as described in protocol section 9.1.6) are AEs recorded on the eCRF where “Is this an adverse event of special interest” is answered as “yes”.

Treatment-emergent AESIs will be presented by the following:

- SOC/PT & by cycle
- SOC/PT & worst grade

A vertical bar plot will be produced showing the number of patients experiencing an AESI presented by worst grade and by cycle.

18.2. DEATHS

If any subjects die during the study as recorded on the “Death” page of the eCRF, the information will be presented in a summary table and a data listing.

18.3. LABORATORY EVALUATIONS

Results from the laboratory will be included in the reporting of this study for Haematology, Chemistry, Virology and Endocrinology. A list of laboratory assessments to be included in the outputs is included in the protocol (section 8.2.2.4 and as a footnote to table 8-6: schedule of assessments).

Presentations will use SI Units.

Quantitative laboratory measurements reported as “< LLOQ”, i.e. below the lower limit of quantification (BLQ), or “>ULOQ”, i.e. above the upper limit of quantification (ULQ), will be converted to the lower limit of quantification (LLOQ) or the upper limit of quantification (ULOQ) for the purpose of quantitative summaries, but will be presented as recorded, i.e. as “< LLOQ” or “>ULOQ” in the listings.

The following summaries will be provided for each lab parameter:

- Actual and change from baseline by visit (for quantitative measurements)
- Worst on-treatment CTCAE grade for each gradable parameter

Document: T:\sas\Debiopharm\Debio_1143\CZA60507\Biostatistics\Documentation\SAP\SAP Text\V5

Author: XXXXXXXXXX Version Number: 5.0
Version Date: 19APR2022

Template No.: CS_TP_BS016 Revision 5
Effective Date: 01Apr2018

Reference: CS_WI_BS005

Copyright © 2009, 2010, 2012, 2016, 2018 IQVIA. All rights reserved. The contents of this document are confidential and proprietary to IQVIA Holdings Inc. and its subsidiaries. Unauthorized use, disclosure or reproduction is strictly prohibited.

- Shift using CTCAE grades from baseline to the worst on-treatment value
- Shift from baseline to the worst on-treatment value using the low / normal / high / (low and high) classification (only for non-gradable parameters)
- Incidence of maximum grade on treatment presented overall and by cycle, updating denominator for each cycle with the number patients receiving at least one dose of nivolumab in that cycle (only for gradable parameters)
- For patients having a grade 3/4 value:
 - Time to First Grade 3/4 Toxicity and Time to Resolution:
 - Time to recovery to grade ≤ 2
 - Time to recovery to grade ≤ 1
 - Time to full recovery (grade 0)
 - Conservative duration: (first assessment showing improvement (lower than grade 3/4) – date when analyte first graded 3/4 + 1)
 - Non-conservative duration: (last date analyte graded 3/4 (before grade ≤ 2) – date when analyte first graded 3/4 + 1)
- Listing of all laboratory data with values flagged to show the corresponding CTCAE grades and the classifications relative to the laboratory normal ranges.
- Listing of notable laboratory abnormalities (i.e., newly occurring CTCAE grade 3 or 4 laboratory toxicities).
- Listing of Pregnancy Test (serum and/or urine).
- Scatter plots showing pre-treatment vs. lowest/highest on-treatment levels will be presented for each laboratory parameter.
- A vertical bar plot showing the worst grade experienced for each parameter

18.3.1. LABORATORY SPECIFIC DERIVATIONS

No specific laboratory derivation will be performed.

18.3.2. LABORATORY REFERENCE RANGES

Quantitative laboratory measurements will be compared with the relevant laboratory reference ranges in SI units and categorized as:

- Low: Below the lower limit of the laboratory reference range.
- Normal: Within the laboratory reference range (upper and lower limit included).
- High: Above the upper limit of the laboratory reference range.

Document: T:\sas\Debiopharm\Debio_1143\CZA60507\Biostatistics\Documentation\SAP\SAP Text\V5

Author: XXXXXXXXXX Version Number: 5.0
Version Date: 19APR2022

Template No.: CS_TP_BS016 Revision 5
Effective Date: 01Apr2018

Reference: CS_WI_BS005

18.3.3. CTC GRADING FOR LABORATORY DATA

Laboratory measurements will be graded using the NCI-CTCAE version 5.0 as defined in the following:

https://ctep.cancer.gov/protocolDevelopment/electronic_applications/docs/CTCAE_v5_Quick_Reference_8.5x11.pdf

For some gradable parameters, the CTCAE can be reassessed by the investigator. For any tables or figures which mention “CTCAE grade” in the sections above, the investigator grade should be used for these parameters.

The following analytes required investigator input:

- Amylase (Increase)
- Lipase (Increase)
- Potassium (increase & decrease)
- Sodium (increase & decrease)
- Hemoglobin (decrease)
- White cell count (Increase)
- Albumin (decrease)
- Calcium (increase & decrease)

These parameter will be flagged in related tables.

